26.5.2 Unanticipated Problems

An Unanticipated Problem is any event, incident, experience, or outcome that is

- 4. unexpected in terms of nature, severity, or frequency in relation to
 - c. the research risks that are described in the IRB-approved research protocol and informed consent document; Investigator's Brochure or other study documents;
 - d. the characteristics of the subject population being studied (persons with life threatening EEbola infection); and

- 5. possibly, probably, or definitely related to participation in the research; and
- 6. places subjects or others at a greater risk of harm (including physical, psychological, economic, or social harm) than was previously known or recognized.

Unanticipated Problems must be reported to the Data Coordinating Center at the University of Minnesota, and local IRB as per local institutional requirements. Unanticipated problems may include problems with protocol implementation, participant safety, and/or concerns regarding informed consent. Initial reports must be sent by e-mail no later than 7 calendar days of site awareness of the event.

Report all Unanticipated Problems that are also SAEs on the SAE CRF.

26.5.3 Pregnancy

Pregnancy itself is not an AE. However, complications of pregnancies are AEs and may be SAEs. Report any complications that are SAEs on the SAE CRF within the above timelines.

Pregnancy outcome data (e.g., delivery outcome, spontaneous or elective termination of the pregnancy) will be on a protocol-specified form. Pregnant participants should be advised to notify their obstetrical care provider of study agent exposure, if applicable.

Reporting Procedures to the IRB

26.6.1 Expedited Reporting to the IRB

SAEs, Serious and non-serious Unanticipated Problems, and deaths will be reported per institutional requirements. Please refer to the Manual of Operations, Reporting SOP about site specific requirements.

26.6.2 Annual Reporting to the IRB

Annual reporting will occur in accordance with institutional requirements.

Follow-Up of Serious Adverse Events

SAEs that have not resolved by the end of the initial follow-up period are followed until final outcome is known. This includes pregnancy. If it is not possible to obtain a final outcome for an SAE (e.g., the subject is lost to follow-up), the reason a final outcome could not be obtained will be recorded by the investigator on the AE CRF (if the CRF is still open) and the SERF.

Sponsor's Reporting Responsibilities

Serious and unexpected suspected adverse reactions (SUSARs) as defined in ICH E6 5.17 and as determined by the IND Sponsor will be reported to FDA, all participating country regulatory authorities, and all participating Investigators as IND Safety Reports.

The IND Sponsor will also submit an IND Annual Report of the progress of the investigation to the FDA and all participating country regulatory authorities.

Safety Oversight

26.9.1 Investigator Safety Monitoring

The Investigator or designee may interrupt the administration of study drug to an individual subject if indicated for unanticipated problems or SAEs. In addition, the Investigators are responsible for:

- Protecting the safety and welfare of subjects
- Evaluating subject safety
- Notifying the sponsor of SAEs and immediately-reportable events
- Informing the IRB/IEC of SAEs, as per institutional requirements

26.9.2 Sponsor Medical Monitor (SMM)

A Medical Monitor, representing the IND Sponsor, has been appointed for oversight of safety in this clinical study.

26.9.3 Data and Safety Monitoring Board (DSMB)

An independent DSMB will review the study no less frequently than twice a year. The DSMB may convene additional reviews as necessary, dependent on the rate of subject accrual. The DSMB will review the study data to evaluate the safety, efficacy, study progress, and conduct of the study. All SAEs, all unanticipated problems, and all IND Safety Reports will be reported by the Data Coordinating Center to the DSMB at the same time they are submitted to the IRB or IND Sponsor. The PI will submit the written DSMB summary open reports with the DSMB recommendations to the IRB.

- The DSMB will monitor safety closely throughout the trial and may pause enrollment in the event of study-related deaths or SAEs that are considered study-related.
- The DSMB will also review the completeness of follow-up and other aspects of study conduct.
- After each meeting they will recommend continuing the study as planned, modifying the study, or terminating the study.

27 CLINICAL MONITORING STRUCTURE

Site Monitoring Plan

As per ICH-GCP 5.18 and FDA 21 CFR 312.50, clinical protocols are required to be adequately monitored by the study sponsor. This study monitoring will be conducted according to the "NIAID Intramural Clinical Monitoring Guidelines." Monitors under contract to the NIAID/Office of Clinical Research Policy and Regulatory Operations (OCRPRO) will visit the clinical research site to monitor aspects of the study in accordance with the appropriate regulations and the approved protocol. The objectives of a monitoring visit will be: 1) to verify the existence of signed informed consent

documents and documentation of the Informed Consent Form (ICF) process for each monitored subject; 2) to verify the prompt and accurate recording of all monitored data points, and prompt reporting of all SAEs; 3) to compare data abstracts with individual subjects' records and source documents (subjects' charts, laboratory analyses and test results, medical progress notes, nurses' notes, and any other relevant original subject information); and 4) to help ensure investigators' are in compliance with the protocol. The monitors also will inspect the clinical site regulatory files to ensure that regulatory requirements (Office for Human Research Protections [OHRP]), FDA, and applicable guidelines (ICH-GCP) are being followed. During the monitoring visits, the investigator (and/or designee) and other study personnel will be available to discuss the study progress and monitoring visit.

28 ETHICS/PROTECTION OF HUMAN SUBJECTS

Informed Consent Process

Informed consent is a process where information is presented to enable persons to voluntarily decide whether or not to participate as a research subject. It is an on-going conversation between the human research subject and the researchers about the essential information about the study, which begins before consent is given and continues until the end of the subject's involvement in the research. Discussions of essential information about the research will include the study's purpose, duration, experimental procedures, alternatives, risks, and benefits, and subjects will have the opportunity to ask questions and have them answered.

The participants will sign the informed consent document prior to any procedures being done specifically for the study. The participants may withdraw consent at any time throughout the course of the trial. A copy of the informed consent document will be given to the participants for their records. The researcher will document the signing of the consent form in the subject's medical record. The rights and welfare of the participants will be protected by emphasizing to them that the quality of their medical care will not be adversely affected if they decline to participate in this study.

Due to the biohazard of Ebola virus contaminated documents, a photograph or scanned image of the informed consent signature page will be stored. No paper copy will be retained.

Subject Confidentiality

All records will be kept confidential to the extent provided by federal, state and local law. The study monitors and other authorized representatives of the Sponsor may inspect all documents and records required to be maintained by the Investigator, including but not limited to, medical records. Records will be kept locked and all computer entry and networking programs will be done with coded numbers only. Clinical information will not be released without written permission of the subject, except as necessary for monitoring by IRB, the FDA, the NIAID, the OHRP, or the sponsor's designee.

29 DATA MANAGEMENT AND MONITORING

Data Management Responsibilities

The Investigator is responsible for assuring that the data collected is complete, accurate, and recorded in a timely manner. Source documentation (the point of initial recording of information) should support the data collected in the electronic data system, and must be signed and dated by the person recording and/or reviewing the data. All data should be reviewed by the Investigator and co-signed as required.

Data Capture Methods

Study data will be collected at the study site(s) as paper CRFs with transmission to the Data Coordinating Center. Data Coordinating Center personnel shall enter data into the electronic database. Corrections to electronic data systems will be tracked electronically (password protected or through an audit trail) with time, date, individual making the correction, and what was changed.

Types of Data

Source documents include, but are not limited to, the subject's medical records, laboratory reports, ECG tracings, x-rays, radiologist's reports, subject's diaries, biopsy reports, ultrasound photographs, progress notes, pharmacy records, and any other similar reports or records of procedures performed during the subject's participation in the study.

Source Documents and Access to Source Data/Documents

Source documents include all recordings of observations or notations of clinical activities, and all reports and records necessary for the evaluation and reconstruction of the clinical trial.

Due to the biohazard of Ebola virus contamination, any original source documents created at the bedside and in the 'hotzone' will be incinerated and not be retained. Where possible, photographs or digital scans will be obtained.

Record Retention

More extensive power tables: Table 13 shows the approximate power for a range of sample sizes and mortality probabilities in the 2 arms, while Table 14 shows the sample sizes required for approximately 80% and 90% power.

Table 13: Approximate Power under Different per Arm Sample Sizes (n) when the Larger and Smaller Mortality Probabilities are pA and pB, Respectively

PΑ PΒ n=20 n=90 n=100 n=30 n=40 n=50 n=60 n=70 n=80 0.1 0.14 0.16 0.24 0.27 0.32 0.38 0.42 0.47 0.51 0.2 0.63 0.93 0.3 0.1 0.35 0.49 0.72 0.79 0.86 0.90 0.95 0.2 0.10 0.14 0.18 0.21 0.24 0.27 0.30 0.34 0.37 0.1 0.61 0.79 0.90 0.95 0.98 0.99 1 1 1 0.4 0.2 0.84 0.27 0.39 0.50 0.60 0.67 0.74 0.80 0.88 0.3 0.08 0.12 0.15 0.18 0.20 0.23 0.26 0.29 0.31 0.1 0.99 0.82 0.95 1 1 1 1 1 1 0.5 0.2 0.99 1 0.49 0.69 0.82 0.89 0.94 0.97 0.98 0.3 0.22 0.35 0.46 0.55 0.62 0.67 0.73 0.79 0.83 0.4 0.08 0.16 0.18 0.20 0.22 0.24 0.26 0.31 0.12 0.1 0.94 0.99 1 1 1 1 1 0.6 1 1 0.2 0.73 0.90 0.97 0.99 1 1 1 1 1 0.3 0.45 0.66 0.80 0.88 0.92 0.95 0.97 0.98 0.99 0.4 0.21 0.35 0.46 0.54 0.61 0.67 0.72 0.75 0.83 0.5 0.08 0.12 0.16 0.18 0.20 0.22 0.24 0.26 0.31 0.1 0.99 1 1 1 1 1 1 1 0.7 1 0.2 0.90 0.99 1 1 1 1 1 1 1 0.3 0.71 0.90 0.96 0.99 1 1 1 1 1 0.4 0.80 0.99 0.45 0.66 0.88 0.92 0.95 0.97 0.98 0.5 0.22 0.35 0.46 0.55 0.62 0.67 0.73 0.79 0.83 0.6 80.0 0.12 0.15 0.20 0.23 0.26 0.29 0.31 0.18

Powers of 80% or higher are boldfaced.

Table 14: Sample Sizes required for 80% and 90% Power for Different Values of the Larger and Smaller Mortality Probabilities, p_A and p_B .

[figure not shown]
p _A	р _в	n ₈₀	n ₉₀
0.2	0.1	198	264
0.3	0.1	61	81
	0.2	293	392
0.4	0.1	31	40
	0.2	81	109
	0.3	357	476
0.5	0.1	19	26
	0.2	39	52
	0.3	95	126
	0.4	392	520
0.6	0.1	13	17
	0.2	23	30
	0.3	41	57
	0.4	97	128
	0.5	392	520
0.7	0.1	10	12
	0.2	15	20
	0.3	22	31
	0.4	41	57
	0.5	95	126
	0.6	357	477

[figure not shown]

[figure not shown]

 	 	 	 	•	 	 	 	 	

Amendment Label	IRB Approval Date	Amendment Summary
A	3/9/15	addition of the Liberian Principal Investigator and study sites. Updated information has been included regarding ZMAPP product and infusion details (three infusion set three days apart). An update of the ongoing conversations of Investigators from all sites has been added to Appendix A.
В	4/6/15	Clarification of the site- specific considerations have been added to the protocol (section 6.15) based on the resources available. Further information from Liberian Ebola Treatment Units has preliminarily identified a correlation between baseline Cycle Threshold (CT) value on Ebola PCR and patient outcomes. This has prompted the Study Team to change the stratification for the randomization procedures of this study
C	4/20/15	The main purposes of the amendment are to acknowledge that the ability of individual sites to perform full spectrum of clinical research components outlined in prior versions protocol varied widely depending upon such factors as staffing, available equipment, and current operational, clinical, and safety practices. Therefore this version of the protocol

SUMMARY of AMENDMENTS TO PROTOCOL

		attempts to define the minimal standards for assessment of efficacy and safety as well as allow full detailed assessments to obtain full longitudinal data collection when sites are able.
D	7/13/15	An updated Investigator's Brochure and an updated version of the ZMAPP Patient Information Sheet was added which will be given to participants at the time of consent.
E	11/23/15	Added long-term follow-up. The DSMB strongly recommended long-term follow-up of enrolled subjects be considered (within reasonable limits of access and feasibility) given reports of the recurrence of Ebola virus disease in some patients. Interested subjects will be offered the opportunity, where and whenever feasible, to participate in long term follow-up (up to 1 year or more depending upon need) past Day 58 of their illness in order to determine whether they are at risk for late onset of any history or symptoms consistent with delayed virologic relapse potentially arising from immunologically-privileged sites.

Data Analysis Plan for MCM RCT

1	STU	JDY OVERVIEW								
2	SUN	JMMARY OF REPORTS								
3	OPE 3.1 3.2 3.3 3.4	Accru Eligib Baseli	4 4 4 5							
4	CLC	CLOSED REPORT TO THE DSMB								
	4.1	1 BASELINE CHARACTERISTICS								
	4.2	DATA (Completeness	6						
	4.3	PRIMA	RY OUTCOME	6						
		4.3.1	Primary analysis at study completion	6						
		4.3.2	Additional analyses	8						
	4.4	Secondary Outcomes								
		4.4.1	Overall Survival	8						
		4.4.2	Time-to-viral load clearance	8						
		4.4.3	Daily Outcomes	9						
	4.5	SAFETY OUTCOMES								
		4.5.1	SAEs							
		4.5.2	Safety listings							
		4.5.3	Pregnancies							
		4.5.4	Infusion Reactions							
		4.5.5	Infusion Interruptions							
		4.5.6	Unanticipated problems							
5	DAI	LY STU	JDY PROGRESS REPORTS ON THE WEB	10						
6	SAE	E REPOI	RTS TO LEAFBIO	10						
7	SHE	ELLS FC	OR TABLES AND FIGURES	10						

31 1 STUDY OVERVIEW

The study protocol serves as the master protocol for the evaluation of multiple candidate countermeasures for the treatment of Ebola virus disease (EVD). The initial phase of the trial will focus on the evaluation of ZMapp and the order of additional treatments to be evaluated is still to be determined.

Participants in the initial phase will be randomized in a 1:1 allocation ratio to optimized standard of care (oSOC) or oSOC plus ZMapp. A maximum of 200 subjects will be randomized (100 per treatment arm) but frequent interim monitoring will be used to allow termination of the trial if a definitive result is achieved early in the trial.

The primary objective of this trial is to establish the safety and efficacy of investigational therapeutics in patients with Ebola virus infection. The primary endpoint for this trial is 28-day survival. Other key efficacy endpoints include: overall survival and time-to-viral load clearance. Safety endpoints

32 2 SUMMARY OF REPORTS

Table A3.1. Type of reports and their distribution

	Prepared			Distributed to			
Reports	by*	Distribution	Frequency [†]	Protocol co-chairs, blinded biostatisticians	DSMB	LeafBio	
Open Report to the DSMB	S	Electronic [‡]	М	X	X	Х	
Closed Report to the DSMB	S	Electronic [‡]	М		X		
Study Progress Reports	S, DM	Web site	Updated daily	X		Х	
SAE Reports							
By trt group	S	DSMB report	М		X		
Pooled **	S	Email	Upon request	X			
SAEs related to treatment	S, SO	Electronic	Event-driven		X	Х	
Safety Reports	S, SO	Electronic	Event-driven	X	X	X	

* Prepared by: DM = data manager, S = Independent biostatisticians,

SO = Safety office at the Statistical and Data Management Center (SDSMB), blinded to study arm

[†] Frequency: M = Prior to each DSMB meeting

[‡]Reports to the DSMB will be available for download from a secure server; upon request, DSMB members will also receive a hard copy. The open report will be posted on the study web site after the DSMB meeting.

** Reports are blinded to study arm assignment. All information will also be provided to the DSMB as part of the closed reports, by treatment group.

Abbreviations: SAE = serious adverse event

3 OPEN REPORT TO THE DSMB

The open report to the DSMB includes reports on accrual, eligibility violations, baseline characteristics, and data completeness as described below. The data are presented pooled across study groups. Open reports will be produced by the independent biostatisticians, under direction of the protocol principal investigators and blinded statisticians.

The open reports will be distributed as indicated in table A3.1, and posted to the study web site after each DSMB review together with the DSMB summary recommendations.

3.1 Accrual

The following reports will be provided:

• Enrollment, by calendar time, geographic location (United States vs. West Africa) and treatment site.

3.2 Eligibility violations

Number (N) and percent (%) of participants who were enrolled in violation of inclusion/exclusion criteria will be reported for each inclusion/exclusion criterion separately and total. Reports will be overall, geographic location (United States vs. West Africa) and by treatment site.

3.3 Baseline Characteristics

The following baseline data will be summarized, overall, by geographic location (United States vs. West Africa) and by treatment site:

- Demographics: Age, sex, race, country of birth, work involving contact with a
 person with Ebola or decedents (N and %), and role (e.g., doctor, nurse,
 ambulance driver, laboratory) and enrollment in any other studies related to
 Ebola
- Clinical Information: Results of pregnancy test, weight, height, blood pressure, pulse, body temperature, respiratory rate and oxygen saturation
- Illness Information: days since onset of symptoms, cycle threshold (actual value and dichotomized as CT > 22 vs. CT ≤ 22), country where EVD diagnosis was confirmed
- Symptoms: Fever, sore throat, cough, etc.
- Chemistries: creatinine and potassium are required, all other chemistries are optional. Optional data will be summarized for subjects where data is available.
- Hematology and Coagulation: optional data summarized as provided.
- Urinalysis: optional data, summarized for subjects where data is available.
- Imaging and Resuscitation: optional data, summarized for subjects where

data is available.

Summaries for continuous-valued outcome will include N and mean, SD or median, IQR. Summaries for categorical outcomes will include N and %.

3.4 Data Completeness

The following reports will be provided, overall, by geographic location (United States vs. West Africa) and by treatment site:

- Withdrawal of consent (N and %)
- Required forms:
 - Number (and % of expected) of completed baseline forms
 - o Number (and % of expected) for each item on the baseline form
 - Number (and % of expected) of daily follow-up forms (overall and by study day)
 - Number (and % of expected) for each item on the daily follow-up form (overall and by study day)
 - Number (and % of expected) of current symptom forms (overall and by study day)
 - Number (and % of expected) for each item on the daily follow-up form (overall and by study day)
 - Number (and % of expected) of daily chemistries forms
 - Number (and % of expected) for each item on the daily chemistries form (overall and by study day)
 - Number (and % of expected) of ZMapp forms (overall and by study day)
 - Number (and % of expected) of completed day 28 forms received, according to the following categories: completed, still in follow-up period, withdrawn and lost to follow-up
 - Number (and % of expected) of completed day 58 forms received, according to the following categories: completed, still in follow-up period, withdrawn and lost to follow-up
 - Number (and % of expected) of discharge forms
 - Number (and % of expected) of death forms
- Optional forms:
 - Number (and % of maximum possible) of completed daily hematology forms
 - Number (and % of maximum possible) of daily urinalysis forms
 - Number (and % of maximum possible) of daily resuscitation forms

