patient per arm, if necessary, up to 20. After that, monitoring would be after every 20 patients per arm until the target number of 100/arm is reached or the trial ends for other reasons. Any decision to curtail for other reasons will be made by a group blinded to trial results. The boundary we recommend is motivated from a Bayesian perspective. Bayesians formulate their prior opinion about the size of the treatment effect through a `prior' distribution, which is updated to a `posterior' distribution after observing data. We give details of the specification of the prior distribution and the construction of the boundary later. What are most important are the boundary itself and its statistical properties such as type I error rate (the probability of crossing the boundary inappropriately, i.e., when the 2 arms are equally effective) and power (the probability of crossing the boundary appropriately, i.e., when one arm is superior to the other).

Table 10 illustrates the design's flexibility by showing the boundaries assuming that factors beyond our control result in only 20 participants per arm by trial's end instead of the planned 100 per arm (stopping boundaries for 100 subjects per arm are included in Appendix B). For example, with 6 people evaluated in each arm, we declare superiority of one arm over the other only if all 6 die in one arm and none die in the other. On the other hand, with 10 people per arm, we cross the boundary if the numbers of deaths out of 10 in the 2 arms are as follows:

- 5. 7 or more and 0,
- 6. 8 or more and 1
- 7. 9 or more and 2
- 8. 10 and 3

Notice that the boundaries at the end of the trial are more lenient than interim boundaries: interim boundaries use a probability level of 99.9%, whereas the final boundary uses a level of 97.5%. This reinforces the need for a blinded group to make stopping recommendations for reasons other than safety or efficacy; otherwise, inflation of the type I error rate could result from lowering the boundary for the final analysis. Boundaries for a sample size of 100 per group will be generated following this same procedure and will be distributed to the DSMB.

Type I Error Rate

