5 DAILY STUDY PROGRESS REPORTS ON THE WEB

Progress reports include reports on accrual, baseline characteristics, and data completeness. These data summaries are pooled across study groups. The reports are similar to those described in the open report section.

These reports will be available on the study web site (controlled access), updated daily. Additional reports may be provided to study leadership on request.

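### The open DSMB report, described as pooled, carries a ZMapp-only form count beside death forms and could partly unblind its readers

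*Combined protocol and SAP*

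**What the plan says.** - **Pooling.** DAP Section 3 says of the open report: "The data are presented pooled across study groups".
- **Content.** The completeness list in DAP 3.4 is broken down "overall, by geographic location (United States vs. West Africa) and by treatment site". It includes "Number (and % of expected) of ZMapp forms (overall and by study day" and, a few lines later, discharge forms and "Number (and % of expected) of death forms".
- **Circulation.** "The open reports will be distributed as indicated in table A3.1, and posted to the study web site after each DSMB review". Table A3.1 names the protocol co-chairs, the blinded biostatisticians, the DSMB and LeafBio for the open report. It names the same readers except the DSMB for the daily progress reports.
- **Web report.** DAP Section 5 says that it covers data completeness, and "The reports are similar to those described in the open report section".
- **Why blinding matters.** Protocol Section 22, Interim Monitoring: "Any decision to curtail for other reasons will be made by a group blinded to trial results". The reason given there is that the final boundary (97.5%) is more lenient than the interim one (99.9%): "otherwise, inflation of the type I error rate could result from lowering the boundary for the final analysis". DAP 4.4.1.3 applies 0.975, in either direction, when the trial ends for external reasons.

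The documents do not name the members of the curtailing group. They do not define the expected number of ZMapp forms, and they do not say that the ZMapp row is withheld from blinded readers.

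**The concern.** A row that exists in one arm only is not blinded by pooling. ZMapp was planned as three infusions three days apart (Final DAP 3.7), and all deaths occurred within 8 days (Final DAP 3.8). The fall in form counts from dose 1 to dose 3 therefore carries information on early deaths in the ZMapp arm, and the total of death forms stands in the same report. The regional split adds a second route: with one patient in the United States (Final DAP 3.8), that region's line shows both arm and outcome.

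At stake is the protocol's error control. Closure for external reasons replaces the 99.9% boundary with the 97.5% boundary at whatever sample size has been reached. That is harmless only if the timing does not depend on the comparison between arms.

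**Working it through.** **1. What the totals reveal.** Let F1 and F3 be the dose-1 and dose-3 form counts and D the total deaths. Let DZ and DS be deaths in the ZMapp and oSOC arms. Split DZ into d0 (before any dose), d13 (between doses 1 and 3) and dL (after dose 3). Let s be dose-3 forms absent for any other reason: stopped, delayed, not yet due or not received.

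- F1 - F3 = d13 + s
- D = d0 + d13 + dL + DS
- D - (F1 - F3) = DS + d0 + dL - s

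Subtraction returns oSOC deaths only if d0 + dL = s. Nothing in the documents ensures this: Final DAP 3.7 allows for patients with no infusion, and dose 3 falls about Day 6-7 while deaths run to Day 8. The inference is real but partial.

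**2. Small units.** 72 patients were randomized between 13 March and 21 November 2015 (Final DAP Section 2). That is 253 days / 72 = 3.5 days per patient over all sites. If the daily web report carries the row, successive by-site snapshots would often differ by one patient. Clustered enrolment and paper-form delays would blur the link.

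**3. The plan's own error rate.** Inputs: uniform(0,1) priors, so the posterior in each arm is Beta(x+1, n-x+1); looks at 6-20, 40, 60, 80 and 100 per arm; thresholds 0.999 interim and 0.975 final, both directions. An exact recursion over deaths per arm gives, at 100 per arm:

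| True mortality, both arms | Protocol Table 11 (simulated) | Exact |
|---|---|---|
| 0.1 | 0.048 | 0.0475 |
| 0.2 | 0.053 | 0.0512 |
| 0.3 | 0.055 | 0.0547 |
| 0.4 | 0.057 | 0.0583 |
| 0.5 | 0.063 | 0.0637 |

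The plan's figures reproduce to within 0.002, with a maximum of 0.064. (DAP 4.4.1.1 gives 0.998 as the interim threshold; the maximum is then 0.071. The rest uses the protocol's 0.999.)

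**4. Full arm knowledge, acted on.** Suppose the trial is closed whenever the 97.5% boundary is crossed at the looks shown:

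| True mortality | Closure at 40, 60, 80 | Closure at 20, 40, 60, 80 |
|---|---|---|
| 0.1 | 0.101 | 0.124 |
| 0.2 | 0.111 | 0.139 |
| 0.3 | 0.114 | 0.138 |
| 0.4 | 0.119 | 0.138 |
| 0.5 | 0.127 | 0.144 |

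These bound closure at those looks. Timing closure at every look from 6 per arm would give 0.14-0.24, but it would need full knowledge throughout and a usable external reason at any moment.

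**5. Partial inference, acted on.** Assume a fraction u of ZMapp-arm deaths occurs before dose 3 and shows as a missing form. The reader estimates ZMapp-arm deaths as visible deaths / u, assigns the rest to oSOC, and closes at 20, 40, 60 or 80 per arm if the inferred split crosses 97.5%. The true data then decide significance. 40,000 simulated trials per case:

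| u (assumed) | Type I, p=0.3 | Type I, p=0.5 | Correlation of inferred with true death difference at 40/arm (p=0.3; p=0.5) |
|---|---|---|---|
| no leak | 0.056 | 0.062 | - |
| 50% | 0.066 | 0.062 | 0.51; 0.44 |
| 75% | 0.079 | 0.080 | 0.71; 0.66 |
| 90% | 0.097 | 0.093 | 0.86; 0.83 |

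The Monte Carlo standard error is about sqrt(0.06 x 0.94 / 40,000) = 0.001. The model lets the reader know u and has no forms missing for other reasons, so it favours the reader.

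**The case against.** The trial is open label (protocol Section 20), so site staff already know their own patients' arms and outcomes, and one readable patient says almost nothing about the treatment difference. That is fair for the lone US patient. It does not cover the totals: the plan still shields aggregate data by arm, through letter-coded closed reports and designated blinded statisticians, and this row goes around that shield.

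Four stronger readings are tempting and not supported.

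- *Mortality by arm can be read off by subtraction.* It cannot: the identity above leaves undosed deaths, late deaths and other missing forms unresolved, and the timing of deaths within the 8 days is not given.
- *The report's readers are the group that may end the trial.* The documents never say so. The study team did receive pooled outcome data when closure was in view (Final DAP Section 2), which makes overlap plausible, no more.
- *The web report certainly shows the row.* Section 5 says only that it resembles the open report.
- *Closure was timed on results.* Final DAP Section 2 ties planned closure to the disappearance of cases. At 72 randomized, about 36 per arm, the looks at 40, 60 and 80 were not reached. The error rates describe the design, not what happened.

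**Conclusion.** The point holds in a limited form. An arm-specific row sits in a report labelled pooled, reaches roles meant to stay blinded and the company LeafBio, and has no stated safeguard. It allows partial inference about early ZMapp-arm deaths, and direct reading of arm and outcome where a site or region has one patient.

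Any effect on error needs three further things: overlap between the readers and the curtailing group, willingness to act, and an external reason available at the right time. Given all three, two-sided type I error is about 0.06-0.10 under partial inference, where the lower end is little or no inflation. With full knowledge it is about 0.10-0.14 for closure at the looks modelled. The 50-90% share of ZMapp-arm deaths before dose 3 is an assumption; the documents give no figure. This is a cheap improvement to blinding, not evidence that the trial's result is compromised.

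**What to change.** - In DAP 3.4 and Section 5, move the ZMapp-form rows (counts, percentage of expected, by study day, by region and by site) to the closed report only. DAP 4.2 already gives completeness by treatment group there, so the DSMB loses nothing.
- In protocol Section 22 and DAP 4.4.1.3, state that whoever decides external curtailment may not see any arm-specific item. Naming that group would make the rule checkable.
- Leave Day 28, death and discharge form completeness by site in the open report. It helps secure the primary endpoint, and once the ZMapp row is gone it no longer stands beside an arm-specific count.

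Cost: wording and report programming. Study leadership loses its open view of infusion-form completeness, which the independent statisticians can query instead.
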